We plan to minimize missing data by avoiding prolonged intervals between stimulations: 2 months may seem long with regard to the literature, but it is a reasonable length of time to be able to determine sustainability of any therapy. To minimize possible biases, analyses will be by intention to treat; any missing data will be addressed with the technique of multiple imputation (Rubin, 2004), generally recognized as best for handling missing data (Little et al., 2012).

Secondary Analyses

For Aim 1, Hypothesis 1b This hypothesis states that A-tDCS+therapy will generalize to other untreated verbs and nouns from baseline to 1 week and 8 weeks post treatment. The analyses will be identical to those described for Aim 1, Hypothesis 1a, except data from untreated verbs (OANBuntrained) and OANBnouns (untrained) will be used.

Aim 1, Hypothesis 1c Hypothesis 1c states that combined A-tDCS+therapy will result in greater improvement in functional communication skills compared to sham+therapy. Changes to functional communication skills resulting from A-tDCS+therapy vs. sham will be assessed using the ASHA FACS scale.

For Aim 2, Hypothesis 1: The proposed study aims to determine which patterns of baseline atrophy will predict the best response to A-tDCS plus a verb treatment using sentence building in individuals with PPA. People with more IFG damage tend to have more trouble with verbs, so we predict they are likely to show the most change in the primary outcome variable (OANBtrained verbs) with A-tDCS+therapy. It is possible that this hypothesis is incorrect, and they will show the least benefit from tDCS due to atrophy in IFG. It may be that people with more atrophy in other areas are going to benefit the most. Confirmation of either hypothesis will help select the best candidates for treatment. The area of peak atrophy (greatest difference between volume of each of the parcels on the JHU-MNI atlas in the participant compared to controls) will be identified for each participant. We will group participants by area of peak atrophy, and compare groups for each outcome variable, using Kruskal-Wallis one-way analysis of variance, for each outcome variable. As an exploratory analysis, we will also evaluate Spearman's correlations between the primary outcome variable and baseline volume in 5 regions of interest (areas affected in PPA: left IFG, left inferior temporal gyrus, left temporal pole, left superior temporal gyrus, and left supramarginal gyrus).

d. *Early stopping rules.* N/A

8. Risks

a. Medical risks, listing all procedures, their major and minor risks and expected frequency.

tDCS

The present study involves application of transcranial direct current stimulation. Weak direct currents can be applied non-invasively, transcranially and painlessly (Nitsche et al., 2003). This is a non-invasive and painless technique that leads to transient changes in cortical excitability that are fully reversible (Nitsche, Liebetanz, Tergau, & Paulus, 2002). There are no known risks of tDCS to other than mild local discomfort at the electrode sites (much less than TMS for example). Several published studies on humans (Gandiga, Hummel, & Cohen, 2006; Nitsche et al., 2003, 2004) reported the following objective safety data:

- No heating of electrodes

- No demonstrable changes in the skin underlying electrode placement after a stimulation period similar to the one proposed in this protocol.
- Mild itching sensation in the absence of pain that never led to stopping a study.
- No change in serum neuron-specific enolase (NSE, marker for neuronal damage) in 5 participants immediately and 1 hour after exposure to 13 min of 1 mA anodal tDCS to motor cortex (Nitsche et al., 2004)
- No changes in diffusion weighted or contrast-enhanced MRI and in EEG after exposure to tDCS

Two reports, one evaluating the safety of tDCS applied in different brain regions in 102 healthy and stroke individuals (Poreisz, Boros, Antal, & Paulus, 2007) and another one investigating the safety of different forms and intensities of tDCS in 103 healthy participants (Iyer et al., 2005), concluded that tDCS is safe and only associated with relatively minor adverse effects in healthy and participants with different neurological conditions. In addition, a double-blind sham-controlled study has shown that comparing tDCS and sham stimulation of the motor cortex elicited minimal discomfort and difference in the duration of tingling sensations. There were no differences in self-rated attention or fatigue, and the study participants or investigators could not distinguish real tDCS from sham (Gandiga et al., 2006). Taken together, all available research suggests that prolonged application should not pose a risk of brain damage when applied according to safety guidelines.

MRI

Participants may undergo MRI scanning in the present study. The effects of undergoing MR scanning have been extensively studied and there are no risks associated with an MR exam. The patient may, however, be bothered by feelings of confinement (claustrophobia), and by the noise made by the magnet during the procedure. They will be asked to wear earplugs or earphones while in the magnet.

b. Steps taken to minimize the risks.

Participants will be carefully screened over the phone prior to being scheduled, to assure that they meet study criteria. tDCS stimulation will be ramped up over the first 30 seconds of stimulation in order to eliminate the sensation of tingling that can occur under the electrodes during the initial moments of tDCS application. The participant may stop testing or the intervention any time. There will be emergency personnel and equipment on hand for the participants' safety.

c. Plan for reporting unanticipated problems or study deviations.

Adverse events will be monitored during the entire visit by the study team. The families will be given telephone numbers of study team as well. The study physician ([name]) will be notified immediately if any adverse events are reported. Adverse events will be monitored until they are resolved or clearly determined to be due to a subject's stable or chronic condition or intercurrent illness. Medical care will be provided, as defined in the informed consent, for any adverse event related to trial participation. Appropriate medical care will include initiating transport to the Emergency Department of The Johns Hopkins Hospital for evaluation when necessary. All adverse events, regardless of intensity or causality, will be recorded in the study documentation and reported to the JHU IRB. Any serious adverse events will be reported to the JHU IRB within 24 hours.

Plan for dealing with incidental findings: MRI scans will be read by a radiologist. If an incidental finding is discovered, the site PI ([name]) will call the patient, and arrange to see the patient in clinic on a timely basis to discuss the finding and the plan for medical follow-up (if any). As [name] is the neurologist of the PPA patients, she will provide care for most of the findings seen on brain MRI, but will refer the patient to neurosurgeons or other physicians as appropriate.

On any given session, if the patient experiences significant frustration, anxiety, or fatigue, that session may be terminated early.

d. Legal risks such as the risks that would be associated with breach of confidentiality.

Participation in this study should not put participants in any legal risk, even in the case of a breach of confidentiality. We will undertake every effort to keep the information in the study confidential. Participants will be assigned a code number for the scans in order to keep the information confidential. The computers on which the information will be stored are password protected. Everybody involved in the study will have completed the appropriate HIPAA training and are fully aware of confidentiality issues. No names will be included in any publications resulting from this work.

e. Financial risks to the participants.

No financial risk is involved. Only participants who are interested in trying word retrieval therapy with tDCS and can be in Baltimore for the therapy as well as the follow-up sessions will participate in the study.

9. Benefits

a. Description of the probable benefits for the participant and for society.

We cannot ensure that this research will provide any direct, sustainable benefit to the participants. It is possible that most participants will benefit from the present therapeutic intervention. Participants may or may not improve from the language therapy, and this improvement may or may not generalize to other items or functions.

Completion of this project will result in better understanding whether and how tDCS coupled with language therapy may help individuals with PPA with their language deficits. This project may provide a way to treat individuals with PPA given that there is no proven treatment available to date.

10. Payment and Remuneration

a. Detail compensation for participants including possible total compensation, proposed bonus, and any proposed reductions or penalties for not completing the protocol.

Participants will not be paid to participate in the study. There is no penalty for not completing a tDCS or MRS session. Given available funding, participants may be reimbursed for parking, gas, meals and hotel expenses that may have occurred during the study

11. Costs

a. Detail costs of study procedure(s) or drug (s) or substance(s) to participants and identify who will pay for them.

There is no cost to the participants for participating in the study.

12. References

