The aim of this proposed study is to study whether the combined benefits of training complex items (building sentences by training verbs and their thematic roles) and applying A-tDCS to left IFG to improve naming will result in significantly greater maintenance and generalization to untreated items and structures, compared to the same training with sham stimulation, in participants with PPA. This study also aims to investigate which patterns of atrophy in PPA are predictive of the best therapy outcomes, which will serve to improve the selection of specific treatments for individual patients in the future. Changes to functional communication skills will also be investigated.

4. Study Procedures

a. *Study design, including the sequence and timing of study procedures (distinguish research procedures from those that are part of routine care).*

Study Procedures Overview

Study design overview: Participants will take part in 2 intervention periods of 15 training sessions (3-5 per week), with either tDCS + language therapy or sham+ language therapy, separated by 2 months. A computer-delivered naming treatment will be coupled with the stimulation. The computer-delivered treatment task will be 45-minutes in total length, so that it will commence at the same time as the tDCS administration and continue for another 25-minutes after the tDCS has ceased. All sessions, with the exception of the optional MRI, may take place at the participant's home or at a Hopkins site. When assessments and intervention are administered at the participant's home a study team member will perform the study procedure at home.

Visit 1: During the first visit, participants will undergo screening assessments. This will include tDCS and MRI safety screening. If the participant passes the initial screening portion, informed consent will be obtained. Neurological examination will also be performed (see below).

Visit 2: Participants may be asked to get MRI scanning, pending funding. Until funding is obtained, we will use MRI scans obtained for clinical purposes within 3 months of enrollment.

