2. Obtain written informed consent: A signed and dated informed consent form will be obtained from each participant before conducting any screening procedures. Participants will be then be assigned a temporary identification number for the purposes of initial screening. All research staff authorized to obtain informed consent will have completed the Miami CITI course in the Responsible Conduct of Research and Protection of Human Subjects prior to their involvement with the study. Furthermore, they will be oriented to the study and trained by the study PI and study co-investigators who have all had extensive training and experience in the ethical and practical aspects of informed consent procedures.
3. Review inclusion/exclusion criteria.
4. Obtain medical history.
5. Conduct neurological examination.

Procedure for MRI Scanning (Visit 2)

Participants may receive MRI scanning to determine site of lesion. MRI will be performed pending funding. We will use clinical MRI (if available within 3 months of enrollment) until funding is obtained.

Procedures for Diagnostic Testing (Visit 3)

Participants will first complete a screening task. This is administered to verify that participants comprehend task requirements. Participants must achieve at least 65% accuracy on screening task (comparable to treatment task) on 1 of 3 attempts to be able to participate in the treatment. If a participant is unable to reach this level of accuracy, study enrollment will be discontinued.

Language and cognitive tests will be administered to participants who pass the screening task. These tests will include:

1. Administer the Western Aphasia Battery-Revised (WAB-R): The WAB-R will characterize the participants' overall language impairment through the evaluation of the main clinical aspects of language functioning, including speech content, speech fluency, auditory comprehension, repetition, and naming. The WAB-R allows for the differentiation of these specific language abilities, as well as the classification of aphasia type. The WAB-R also yields a composite score, the Aphasia Quotient, which provides an overall measure of severity, in which lower scores denote more severe aphasia (Kertesz, 2007). Experimenters will refer to the manual for explicit instructions regarding administration and scoring procedures. Administration time will range between 30-45 minutes.

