- 3) Not medically stable
- 4) Picture naming ability below 10%
- 5) Picture naming ability above 85%
- 5) Significant history of drug or alcohol abuse or psychiatric or neurologic problems affecting the brain (other than PPA)
- 6) Non-MRI compatible pacemaker, implanted ferrous metal, claustrophobia, or other MRI contraindication
- 7) Seizures during the previous 12 months
- 8) Uncorrected visual loss or hearing loss by self-report
- 9) Use of medications that substantially lower the seizure threshold (e.g., methylphenidate) or use of NMDA antagonists (e.g., memantine)
- 10) History of brain surgery or any metal in the head
- 11) Scalp sensitivity (per participant report).

6. Drugs/ Substances/ Devices

a. The rationale for choosing the drug and dose or for choosing the device to be used.

tDCS has been established as a valid and reliable tool for at least temporarily affecting brain and behavior with minimal risks. Stimulation will be delivered by a battery-driven constant current stimulator (Soterix device, or a comparable model). The stimulator is not connected to a mainline power source and cannot produce in excess of 4mA of current. We will use non-metallic, conductive rubber electrodes covered by

Date: 01/11/2019
Principal Investigator: [name]
Application Number: IRB00174879

saline-soaked sponges to minimize the potential for chemical reactions at the interface of the scalp or skin and the electrodes.

b. *Justification and safety information if FDA approved drugs will be administered for non-FDA approved indications or if doses or routes of administration or participant populations are changed.*
N/A

c. *Justification and safety information if non-FDA approved drugs without an IND will be administered.* N/A

7. Study Statistics

a. Primary outcome variable

The primary outcome variable will be trained verbs on the OANB (OANBtrained) (pre-treatment and 1-week post-testing). To assess change in naming ability, the primary outcome in this study, the OANB) will be administered.

b. Secondary outcome variables

We will evaluate the effect of tDCS versus sham on change in naming of untrained verbs and nouns, and determine which pattern of atrophy is associated with the best treatment outcome.

c. Statistical plan including sample size justification and interim data analysis

Statistical Analyses

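### Aim 2 may pool clinical and research MRI scans with no term for scan source; if both are used, this weakens the exploratory atrophy-response correlations and could confound them

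*Combined protocol and SAP*

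**What the plan says.** **Where the scans come from.** Section 4a, Study Procedures Overview (Visit 2), makes the research scan conditional: "Participants may be asked to get MRI scanning, pending funding". Before that point, "Until funding is obtained, we will use MRI scans obtained for clinical purposes within 3 months of enrollment". The same section describes the session locations "with the exception of the optional MRI". The later paragraph on MRI scanning at Visit 2 adds that a clinical scan may not exist: "We will use clinical MRI (if available within 3 months of enrollment) until funding is obtained". Section 7c expects at least 50 participants to be enrolled over five years, with 45-50 completing.

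**How the scans are used.** Section 7b lists among the secondary outcomes to "determine which pattern of atrophy is associated with the best treatment outcome". Section 7c (Secondary Analyses, Aim 2) defines each participant's peak atrophy as the "greatest difference between volume of each of the parcels on the JHU-MNI atlas in the participant compared to controls". The group analysis is: "We will group participants by area of peak atrophy, and compare groups for each outcome variable, using Kruskal-Wallis one-way analysis of variance". As an exploratory step it adds Spearman "correlations between the primary outcome variable and baseline volume in 5 regions of interest".

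**What is not stated.** The plan gives no acquisition standard for clinical scans and no description of the controls' scans. It has no harmonisation step, no covariate or stratum for scan source, and no sensitivity analysis by source.

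**The concern.** MRI is the only source of the Aim 2 predictor. The plan allows that source to change on a calendar event, the arrival of funding, inside a five-year enrolment. If clinical and research acquisitions give systematically different parcel volumes, part of the pooled variation in volume reflects how a participant was scanned and not how much tissue was lost.

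Two consequences follow, under different conditions:

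- **Noise.** An offset between sources inflates the variance of each regional volume and weakens a true volume-response correlation. This needs only the offset.
- **Confounding.** If response also differs between early and late enrollees, for example through case mix, then source is related to both volume and response, and a correlation can appear where none exists. This needs the offset and a drift in response.

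The secondary objective is to guide the choice of treatment for individual patients from their atrophy pattern, so a weakened or spurious relation would bear on that use.

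**Working it through.** **The plan's own figure.** There is no sample-size or power figure for Aim 2. The only one is for Aim 1: a two-sample t-test with effect size 0.6 and 80% power (two-sided 5% assumed, as alpha is not stated) needs 45 per condition, and 45 / 0.90 = 50, as stated. It enters here only as the number of completers, 50 × 0.90 = 45.

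**Assumptions not in the documents.** All 45 completers have a scan, half from each source. Clinical and research volumes differ by *d* within-source SDs (0.5 to 1). Response differs by *e* SDs between the two enrolment eras (0, 0.5 or 1), and source follows era. Tests are two-sided at 5%.

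**Step 1: noise.** With a 50:50 mix the between-source variance is d²/4, so a true correlation r becomes r / √(1 + d²/4). Power uses Fisher's z with Spearman variance 1.06/(n − 3) = 1.06/42. The simulated column is from 4,000 trials per setting.

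| d | factor | r = 0.40 becomes | power, formula | power, simulated | simulated, adjusted for source |
|---|---|---|---|---|---|
| 0 | 1 | 0.40 | 76% | 74% | 73% |
| 0.5 | 0.970 | 0.39 | 73% | 72% | 73-74% |
| 1 | 0.894 | 0.36 | 65% | 62% | 73% |

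The loss is about 2-3 points at 0.5 SD and about 11 points at 1 SD.

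**Step 2: confounding of the Spearman correlations.** With no true relation, the induced correlation is (d·e/4) / √[(1 + d²/4)(1 + e²/4)]. For d = 1, e = 0.5: 0.125 / √(1.25 × 1.0625) = 0.11. For d = 1, e = 1: 0.25 / 1.25 = 0.20. The simulated mean Spearman values are 0.112 and 0.198. Simulated type I error:

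| d | e | unadjusted | adjusted for source |
|---|---|---|---|
| 0.5 or 1 | 0 | about 5% | about 5% |
| 0.5 | 0.5 | 6.6% | 5.1% |
| 0.5 | 1 | 10.5% | 4.7% |
| 1 | 0.5 | 11.0% | 4.9% |
| 1 | 1 | 25.9% | 5.1% |

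**Step 3: the peak-atrophy label.** The label is the parcel with the largest difference, so an offset equal in every parcel changes no label. With five independent parcels, an offset confined to one parcel of 0.25, 0.5 or 1 SD relabels 6%, 13% or 29% of the affected participants.

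**Step 4: the Kruskal-Wallis test.** Five parcels, no true relation, 1 SD offset, simulated rejection rates:

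| Offset pattern | e = 0.5 | e = 1 |
|---|---|---|
| equal in all parcels | 4-5% | 4-5% |
| one parcel only | 4.0% | 7.9% |
| random by parcel (SD 1) | 6.7% | 15.7% |
| Spearman, for comparison | 11.0% | 25.9% |

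**Step 5: what a binary source term leaves behind.** If clinical scans also differ among themselves (SD 1, assumed), then with r = 0.40 and d = 1 power is 51% unadjusted and 57% adjusted, against about 72% with no scanner effect.

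**The case against.** The strongest reply is that the switch may never happen. The research scan depends on funding and is optional. If funding never comes, or comes before the first participant, there is one source. If it comes midway, some later participants may still have only a clinical scan, or none. A reader might infer that the source will change partway and that source and enrolment date will coincide; the documents support neither as a certainty. This stands, and the point is therefore conditional.

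Second, a reader might infer that a scanner shift would mislabel peak atrophy for everyone enrolled in one era. The definition does not support that: a uniform shift relabels nobody, a one-parcel shift relabels a minority at the offsets examined, and no document indicates a parcel-specific shift.

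Third, a reader might carry the inflated Spearman error over to the main Aim 2 test. The correlations are labelled exploratory, and the Kruskal-Wallis test is much less affected (Step 4).

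Fourth, false positives need a drift in response that no document describes. The Aim 2 statement in Section 2 contrasts A-tDCS with sham. If response is scored as that within-person contrast, drift common to both periods cancels. Section 7c is less clear on the scoring, so this reduces the risk without removing it.

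What the reply does not remove is the gap itself. The plan provides for two sources and has no step for the case in which both are used. Clinical scans may also differ from one another and from the controls' scans, so recording the acquisition is useful even without a switch.

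**Conclusion.** The concern holds in conditional form. If funding arrives during enrolment, both sources are used, and their volumes differ, the unadjusted Spearman correlations lose about 2-11 points of power for a true correlation of 0.4 at offsets of 0.5-1 SD. If response also drifts by 0.5-1 SD, their type I error rises to about 7-11% at a 0.5 SD offset and 11-26% at 1 SD. Without drift it stays near 5%. The Kruskal-Wallis comparison responds only to parcel-specific offsets, and less strongly.

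These sizes illustrate a range: the offset, the drift, the even split and the 45 scanned completers are all assumptions. Only Aim 2 is touched. A reader might infer that the primary tDCS-sham comparison of trained-verb naming is compromised; it uses no MRI value, so it is not. This is an inexpensive improvement to a secondary analysis and not a flaw in the trial's main conclusion.

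**What to change.** Add to Section 7c, Aim 2, before outcome data are examined:

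- Record for each participant the scan source (clinical or research), scanner and sequence.
- If both sources occur, make the stated exploratory analysis a partial Spearman correlation adjusted for source.
- If both sources occur, repeat the Kruskal-Wallis comparison as a sensitivity analysis, either with outcomes ranked within source or in the larger single source.
- Describe the controls' scans, and compare volumes with controls from a comparable acquisition where such controls exist.

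The cost is SAP wording, a few recorded fields and one degree of freedom, with no added visits or participants. There are two limits. Source-by-parcel groups may be too small for the within-source comparison to say much. A binary source term also leaves differences among clinical scanners in place, which is why scanner and sequence should be recorded as well.
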